5.12.3 Replacement of withdrawn participants

Participants who withdraw from the trial will be replaced in certain circumstances, and each case will be assessed individually.

A participant who is withdrawn in any of the following situations may be replaced:

- The participant is withdrawn from the trial prior to attending the next visit following their baseline assessment.
- The participant is found to be pregnant during the baseline assessment.
- The safety bloods taken at baseline show that the participant is ineligible for the trial.

5.13 End of Trial

The end of the clinical trial is defined as the final participant's 24-week follow-up visit being completed and all blood samples analysis for the final visits being completed. All data queries will be resolved, as far as possible, before the database is locked. The Sponsor, CI and the TSC have the right at any time to terminate the trial for clinical or administrative reasons.

The end of the trial will be reported to the Sponsor, Research Ethics Committee (REC), Regulatory Authority (RA) and NHS R&D Office(s) within 90 days, or 15 days if the study is terminated prematurely. It is the CI's responsibility to ensure that any appropriate follow-up is arranged for all participants; this will be delegated to the site PIs.

A final report will be provided to the Sponsor, REC, MHRA and Funder within one year of the end of the study.

Subject to funding a substantial amendment may be submitted to cover longer term follow of participants.

6. SUB-STUDIES PROCEDURES

6.1 Mechanistic sub-study

In addition to the research bloods collected for all participants, a subset of patients will be asked to consent to provide additional blood samples

6.1.1 Newcastle Mechanistic Cohort

Participants from the Newcastle site only who are enrolled in the ECP+SOC arm will be invited to provide additional blood samples immediately pre and post treatment cycle of ECP on 3 occasions. This will allow for analysis of immune tolerance and apoptotic cells throughout ECP treatment.

During the recruitment process for the main trial, participants from this site will be asked to consent to participate in this additional research blood sampling.

The following research bloods sample, will be taken immediately before ECP on day 1 and immediately after ECP on day 2 of ECP treatment cycles 1, 7 and 9 (week 0, 12 and 20).

- 20ml of whole blood in two EDTA tubes before ECP on day 1
- 20ml of whole blood in two EDTA tubes after ECP on day 2

Processing of blood samples at site:

- Tubes should be mixed immediately after collection by gentle inversion 8-10 times.
- Samples should be stored between 2-5 C in a fridge
- The laboratory staff should be contacted to arrange immediate collection

Note: Where possible please notify the laboratory staff prior to the sample collection to allow for immediate collection and transfer to the processing laboratory at Newcastle University.

6.1.2 Mechanistic Outcome Measures

Research blood samples will be collected for molecular and cellular analysis of peripheral blood during the study. The outcome measures are as follows:

- The serum concentration of key immune markers including pro-inflammatory and anti-inflammatory cytokines, chemokines, and growth factors.
- The number, % and phenotype of circulating lymphocytes, monocytes, and dendritic cells detectable in blood.
- Transcriptional assessment of genes encoding effector molecules and immunosuppressive cytokines in leucocytes including T-lymphocytes.
- The % of circulating dendritic cells exhibiting a tolerogenic phenotype with reduced expression of co-stimulatory molecules in pre and post ECP samples.
- The number, % and suppressive capacity of regulatory T-cells in pre and post ECP samples.

6.1.3 Storage and Analysis of Research Blood Samples

Please see the E-CLAD UK laboratory manual for further details about the storage, labelling and shipping of all research bloods.

It is the responsibility of the trial site to ensure that samples are appropriately labelled in accordance with the trial procedures to comply with the applicable legislation UK Data Protection Act 2018 and the UK GDPR as amended on 01 January 2021 by regulations under the European Union (Withdrawal) Act 2018, to reflect the UK's status outside the EU. Biological samples collected from participants as

part of this trial will be transported, stored, accessed, and processed in accordance with national legislation relating to the use and storage of human tissue for research purposes and such activities shall at least meet the requirements as set out in the 2004 Human Tissue Act and 2006 Human Tissue (Scotland) Act.

All shipments of biological samples will be labelled and shipped according to local legislation.

A full chain of custody is maintained for all samples throughout their lifecycle. Please refer to the E-CLAD UK Laboratory Manual for further details.

The site is responsible for keeping full traceability of biological samples from the time the samples are collected from the participant, whilst in storage at the site until shipment. The site also needs to keep documentation to confirm receipt of samples shipped to analytical laboratories.

The sample receiver (analytical laboratory) is responsible for keeping full traceability of the samples received, whilst in their storage and during use until analysed, shipped, or disposed of.

The samples will be used up or disposed of after analyses or retained for further use as described below.

The sponsor keeps oversight of the entire sample life cycle through monitoring of the trial sites and analytical laboratories.

6.2 Qualitative Interview sub-study

A 24-month sub-study will involve up to 30 participants who consent to individual semi-structured interviews conducted by an experienced qualitative research associate. The purpose of these interviews is to understand patient perceptions, acceptability, and experiences of living with CLAD and of experiencing ECP therapy. This sub-study format is guided by the patient and public involvement (PPI) group consulted for this trial. Twenty participants in this sub-study will have undergone ECP.

During the recruitment process for the main trial, participants from across all five trial sites will have been given the option to consent to being contacted about the qualitative sub-study. From this pool of positive responses, the qualitative research team will engage in a process of purposive sampling, aiming to achieve variation across the sample in terms of age, gender, location (e.g., distance from treatment centre), length of time living with and stage of CLAD. Pseudonymised health data from the trial database will be provided to the qualitative research team. These categories are likely to have an impact on participants' experiences and were informed by consultation with the PPI panel. Any participants not selected for interview will be provided with a 'Thank you for volunteering' letter which will be distributed by sites. The qualitative research team will advise sites of participants not selected for interview.

Prior to contacting those who expressed an interest in participating in the qualitative interview sub-study, the team will check with site PIs or co-PIs as to the health status of the participant to ensure contact is appropriate. Selected participants will be provided with the qualitative sub-study PIS via email, post or at their next suitable study visit by the research team at sites. The qualitative sub-study PIS will provide potential participants with the option to contact the qualitative research team themselves if they wish, for further information or to express their decision to participate or not. Alternatively they can choose to wait for the qualitative research team to contact them. The qualitative team will respond via email or telephone to those participants that contact them about the interviews. Those who no longer wish to participate will not be contacted about the qualitative sub-study again. Those who wish to consider participation will be given time (approximately a week) to consider the information before being contacted by the qualitative team. Some participants may wish to arrange a time for an interview during the initial contact with the qualitative researcher and

this will be accommodated. The researcher will confirm that the PIS has been read, considered and understood, and that they still wish to participate prior to formal data collection commencing. Participants will be given the opportunity to ask questions prior to providing consent. Consent for the qualitative interview sub-study will be collected remotely. Participants may wish for a family member, friend, or carer to be present during the interview. Such requests will be accommodated, and the third party provided with an information sheet and consented prior to the interview commencing.

Participants will be interviewed in their own home, either by Zoom, Skype (or similar web-based technologies) or by telephone. This will allow greater inclusivity of participants and reduce travel time. Interviews will take place any time before a participant's 24 week follow up. This will allow the capture of patient experience at a range of different time scales. All interviews will be audio-recorded and transcribed verbatim.

As there will be a lag between participants initially consenting to the main study (and indicating at that stage if they would like to take part in an interview) and the interviews being conducted, a qualitative withdrawal form is available for any participants that subsequently change their mind. If a participant indicates to their research team that they no longer wish to take part in an interview, this withdrawal form should be completed, and the central trial management team informed of this so that the participant is not contacted any further regarding an interview.

Those who do not wish to take part in a structured interview in the sub-study will still be able to participate in the main study. Those who do participate will be able to withdraw from the qualitative interview sub-study at any time, without giving a reason. This will not impact their involvement in the main trial.

6.3 Health Economic Sub-study

A health economic evaluation will be undertaken at the end of the trial. No additional assessments will be performed by the patient as all data regarding patient treatment, interventions and hospitalisations are already collected in the ECRFs throughout the participant's involvement in the trial.

7. DEFINITIONS

CLAD is to be defined in line with the 2019 consensus report from the Pulmonary Council of the ISHLT (3).

7.1 Stages of CLAD

Stage	Spirometry
CLAD 0	Current FEV1 > 80% FEV1 baseline*
CLAD 1	Current FEV1 > 65 - 80% FEV1 baseline*
CLAD 2	Current FEV1 > 50 - 65% FEV1 baseline*
CLAD 3	Current FEV1 > 35 - 50% FEV1 baseline*
CLAD 4	Current FEV1 < 35% FEV1 baseline*

*Baseline defined as average of the two best post-operative FEV1 measured ≥ 3 weeks apart

7.2 Phenotypes of CLAD

7.2.1 Bronchiolitis Obliterans Syndrome (BOS):

1. Persistent $\geq 20\%$ decline in FEV1 compared to best-achieved baseline[~]
2. Obstructive spirometry with FEV1/FVC < 0.7
3. Absence of persistent pulmonary opacities on chest imaging (chest X-ray and/or computed tomography).

[~] defined as average of the two best post-operative FEV1 measured ≥ 3 weeks apart

7.2.2 Restrictive Allograft Syndrome (RAS)

1. Persistent $\geq 20\%$ decline in FEV1 (+/- FVC) compared to "best-achieved" baseline
2. Decrease $\geq 10\%$ in total lung capacity (TLC) compared with "best-achieved" baseline*
3. Persistent opacities on chest imaging (chest X-ray and/or computed tomography)

*defined as the average of the two best TLC measurements obtained at the same time as or very near to the best 2 post-operative FEV1 measurements. In the absence of best-achieved TLC measurements, a decline of FVC of $\geq 20\%$ compared to baseline can be used as a surrogate for restriction if additionally, Spirometry shows FEV1/FVC > 0.7.

7.2.3 Mixed and Undefined CLAD Phenotypes

CLAD Phenotype	Obstruction	Restriction	CT Opacities
BOS	Yes	No	No
RAS	No	Yes	Yes
Mixed	Yes	Yes	Yes
Undefined	Yes	No	Yes
	Yes	Yes	No

Obstruction is defined by a fall in FEV1 (as described above) and associated with other indices of airflow limitation (FEV1/FVC ratio < 0.70). Restriction is properly defined as a $\geq 10\%$ reduction in baseline TLC. CT Opacities refers to parenchymal opacities and/or increasing pleural thickening consistent with a diagnosis of pulmonary and/or pleural fibrosis and likely to cause a restrictive physiology, rather than the airway-based changes consistent with bronchiectasis. Although opacities and bronchiectasis may coexist, in some cases, the presence of bronchiectasis may reflect traction changes on airways due to fibrotic parenchymal opacities.

Mixed phenotype exhibits elements of both BOS and RAS and, all cases that transition from a BOS phenotype to an RAS phenotype and vice-versa, will meet these criteria.

Undefined means definite CLAD, but with 2 possible combinations of variables, making it difficult to categorize in the upper panels (BOS, RAS, or mixed phenotype). For the purposes of Phenotype classification in the trial then Undefined will be combined with mixed in terms of randomisation.

7.3 Lung Function

Lung function stabilisation – defined as a less than or equal to a 10% loss in FEV1 and FVC from study baseline to 24 weeks.

Rapid decline – defined as a greater than 20% fall in FEV1 or FVC in the first 12 weeks from study baseline.

Non-responders – As outlined in the study flow chart in Section 3.3, a non-responder is defined as someone who experiences a decline in FEV1 or FVC of more than 10% at 24 weeks compared to baseline readings due to progressive CLAD. A non-responder may also be someone with a decline in FEV1 or FVC of >20% within 12 weeks of the baseline visit that is confirmed as being due to progressive CLAD.

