2. OBJECTIVES AND OUTCOME MEASURES

2.1 Primary Objective

To determine if ECP therapy plus SOC is more effective at stabilising lung function in lung transplant recipients with CLAD compared to SOC alone.

Lung function stabilisation will be derived from change in FEV1 and FVC at 12 and 24 weeks compared to baseline at study entry. The primary outcome measure is a composite responder outcome, which is defined as both 'lung function stabilisation' from baseline to 24 weeks and 'no rapid decline' as measured from baseline to 12 weeks (see section 7 for definitions).

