5.3.3 Blinding

This trial is unblinded. Study participants, clinicians and the NCTU team will be aware of treatment allocation. The Statistical Analysis Plan (SAP) will be developed by statisticians who are unaware of

treatment allocation and will be finalised and signed-off prior to unblinded data being reviewed by the DMC. The SAP will contain full details of the final analyses, with details of who will perform these analyses. Trial statisticians will have access to unblinded data for the purposes of creating DMC reports. No other members of the research team will have access to the unblinded data contained in closed DMC reports, unless the DMC request that unblinded information is released. In the case that a major amendment is proposed to the SAP, this will be approved by an appropriate blinded independent statistician (the independent Trial Steering Committee statistician or an appropriate senior member of the Biostatistics Research Group).

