5.5 Identification of Non-Responders

As E-CLAD UK is an intervention study with an efficacy endpoint, it is very important that every possible effort is made to allow participants to safely complete the study as *per protocol*. The aim of this study is to determine if ECP is efficacious in stabilising CLAD and therefore it is critical that sufficient ECP treatment is given to participants in the treatment arm to perform this assessment. All participants will be assessed at 12 weeks to assess response and identify non-responders in both groups.

If there is a >20% fall in FEV1 or FVC from baseline either within or at the 12-week assessment, then it is important for site PIs to confirm if this is due to progressive CLAD and not an intercurrent infection, new or progressive large airway obstruction or an extra-pulmonary cause. Participants can only be identified as a non-responder when a >20% fall in FEV1 or FVC is confirmed as being due to progressive CLAD. If there is any doubt that the >20% fall in FEV1 or FVC is due to progressive CLAD, then the participant should remain in the study and possible other causes should be fully treated and lung function reassessed at a suitable interval not exceeding the next study visit.

For any participants where CLAD progression means further rescue treatment is required which is not standard of care for patients suffering from CLAD (for example TLI), it is important to note that these participants must be withdrawn from the E-CLAD UK trial prior to any rescue treatment being given.

A decision Tree is provided in Appendix 6 regarding identifying non-responders and whether they are able to continue in the trial depending on their circumstances.

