10.3 Statistical Analyses

10.3.1 Analysis of the Primary Outcome Measure

The primary and secondary analyses of the primary outcome will be conducted using the augmented binary method (22). This will utilise a joint model of the change in FEV1 and FVC from baseline to 12 and 24 weeks, leveraging this to estimate the difference in probability of being a responder (no 'rapid decline' at 12 weeks and $\leq 10\%$ loss in FEV1 and FVC at 24 weeks) between the treatment arms. In addition to an estimated difference, the method will provide a confidence interval for the difference and a p-value for significance testing. The method allows covariates to be adjusted for: we will include the variables included in the stratified randomisation routine as covariates (CLAD phenotype and site).

Sensitivity analyses of the primary outcome will be conducted using a logistic regression model for the binary responder primary outcome, adjusting for CLAD phenotype and site. A second sensitivity analysis will include all participants who had $>20\%$ reduction from baseline in FEV1/FVC at 12 weeks as non-stabilised.

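### The protocol is inconsistent on whether an unblinded judgement of cause enters the primary endpoint

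*Protocol*

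**What the plan says.** **The endpoint.** Protocol section 2.1 gives a composite responder outcome, "defined as both 'lung function stabilisation' from baseline to 24 weeks and 'no rapid decline' as measured from baseline to 12 weeks", and points to section 7 for the terms. In section 7.3 stabilisation is "defined as a less than or equal to a 10% loss in FEV1 and FVC from study baseline to 24 weeks" and rapid decline is "defined as a greater than 20% fall in FEV1 or FVC in the first 12 weeks from study baseline". Neither has a condition on cause. Section 10.3.1 repeats the same rule for the augmented binary analysis. That analysis models change in FEV1 and FVC jointly, and the only covariates it names are phenotype and site.

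**The label.** Section 7.3 then defines a non-responder at 24 weeks by a "decline in FEV1 or FVC of more than 10% at 24 weeks compared to baseline readings due to progressive CLAD", with a parallel 12-week rule for falls above 20% confirmed as CLAD. Sections 3.1, 5.5.1 and 5.5.2 use the CLAD condition for the 12-week rule. Section 5.5 is the most explicit: "Participants can only be identified as a non-responder when a >20% fall in FEV1 or FVC is confirmed as being due to progressive CLAD". It is also the section that says who decides: "it is important for site PIs to confirm if this is due to progressive CLAD and not an intercurrent infection".

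**The links between them.** Section 5.5.3 says that non-responders are censored and counted as not stabilised in the primary endpoint analysis. Section 10.3.1 adds: "A second sensitivity analysis will include all participants who had" a reduction above 20% at 12 weeks, all of them counted as not stabilised. Section 5.3.3 states: "Study participants, clinicians and the NCTU team will be aware of treatment allocation".

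**The concern.** A responder is defined by spirometry. A non-responder is defined by spirometry plus an attribution of cause. The two terms are therefore not complements, yet section 5.5.3 feeds the second into an endpoint built on the first, and section 10.3.3 uses responder and non-responder as the two levels of one variable.

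If attribution decides whether some falls count, then a site investigator who knows the arm has a say in the primary outcome. Deciding whether a fall is infection or progressive CLAD involves clinical judgement, and the protocol describes no blinded or independent adjudication of cause. At stake is whether the primary comparison rests on measurements only, or partly on open-label judgement.

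**Working it through.** **1. The definitions applied to each type of participant.** The spirometric rule is that of sections 2.1, 7.3 (stabilisation, rapid decline) and 10.3.1. The attributed label is that of sections 3.1, 5.5 and 7.3 (non-responder).

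| Week 12 | Week 24 | Judged cause | Spirometric rule | Attributed label |
|---|---|---|---|---|
| fall ≤20% | loss ≤10% | – | responder | not a non-responder |
| fall >20% | any | CLAD | failure | non-responder |
| fall >20% | loss ≤10% | not CLAD | failure | not a non-responder |
| fall ≤20% | loss >10% | CLAD | failure | non-responder |
| fall ≤20% | loss >10% | not CLAD | failure | not a non-responder |

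The rules disagree in rows 3 and 5.

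- Row 3 is the main case. The 24-week value meets the stabilisation limit, so the outcome turns on whether the earlier fall counts. If the primary analysis uses the attributed label for the 12-week component, this participant becomes a responder.
- Row 5 is a gap in the labels. The participant is neither stabilised nor a non-responder, but sections 2.1 and 10.3.1 still make the outcome a failure.

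**2. What the second sensitivity analysis implies.** Under the spirometric rule every fall above 20% at week 12 is already a failure. An analysis that counts all such falls as not stabilised would then classify nobody differently. It classifies someone differently only if the primary analysis leaves some of these falls uncounted, and the falls for which the protocol gives a reason to do so are those judged not to be CLAD (row 3). This is an inference from the text; the protocol does not say it outright. No matching sensitivity analysis is stated for the 24-week component.

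**3. The plan's own figure.** The point does not depend on it. Section 10.1 has 90 patients 1:1, so 90/2 = 45 per arm, response rates of 55% and 30%, one-sided 5% and 80% power. By the unpooled normal approximation, power = Φ(0.25 / √[(0.55×0.45 + 0.30×0.70)/45] − 1.645) = Φ(2.479 − 1.645) = 79.8%. The pooled version gives 78.2%. Exact enumeration of Barnard's test gives 76.9% to 77.8%, depending on how outcomes are ordered. The stated figure is reproduced approximately.

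**4. Illustration of sensitivity to single participants.** One participant is 1/45 = 2.2 percentage points of an arm. The planned SOC rate gives 0.30×45 = 13.5 responders, so take 14. Barnard's test, one-sided, 45 per arm:

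- 22 v 14: p = 0.047
- 21 v 14: p = 0.071

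The difference needed is not constant. Differences of 7 (14 v 7) and 5 (7 v 2) are significant, while a difference of 8 at 24 v 16 is not (p = 0.0503). Barnard's test is the sample-size assumption in section 10.1; the planned primary analysis is the augmented binary method.

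**The case against.** The strongest reply is that responder has one definition, given consistently in 2.1, 7.3 and 10.3.1, and that non-responder is a clinical label governing rescue treatment and withdrawal. Section 5.5.3 also runs one way: it makes attributed non-responders failures, which the spirometric rule does anyway, and does not say that other participants with a fall count as stabilised. The protocol has safeguards too. In case of doubt the participant stays in, other causes are treated and lung function is reassessed by the next visit (5.5). Discussion with the chief investigator is recommended for falls before 12 weeks (5.5.1, 5.5.2). Home readings are not to be definitive for classifying non-responders (5.8).

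Much of this stands, and it narrows the point. It does not remove it. Section 5.5.3 names the primary endpoint analysis, so the label is not purely clinical, and the second sensitivity analysis has no purpose on the purely spirometric reading. None of the safeguards is blinded adjudication.

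Three stronger readings are tempting and are not supported:

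- A reader might infer that a 24-week loss put down to infection can be turned into a response. No section makes a loss above 10% at 24 weeks a response.
- A reader might infer that eight participants is the general threshold for significance, or that one re-attribution would flip the planned result. Both rest on one control count and on a test that is not the planned analysis.
- A reader might compute an inflated type I error by excusing a share of all ECP-arm failures. That would include 24-week failures that nothing in the protocol excuses.

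Section 5.6 also lets belief about cause postpone the week 24 visit by up to 30 days. That changes when the value is measured, not how it is classified, and is a separate matter.

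**Conclusion.** The inconsistency is real and lies in the protocol's own text. Responder status is spirometric in 2.1, 7.3 and 10.3.1. The non-responder label depends on cause, enters the primary analysis through 5.5.3, and is presupposed by the second sensitivity analysis. The live ambiguity is mainly the participant with a fall above 20% by week 12, judged non-CLAD, who has lost 10% or less at week 24. At 24 weeks the fault is a gap between labels.

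Because clinicians know the allocation, attribution could bias the endpoint. How many participants would be affected, and in which direction, cannot be derived from the document. The Barnard figures show only that single classifications can matter near the boundary when the SOC arm has 14 responders of 45. A statistical analysis plan, not seen here, may settle the coding, but it would have to choose between two rules that the protocol states.

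**What to change.** State in sections 5.5.3, 7.3 and 10.3.1 that responder status in the primary analysis is set by measured FEV1 and FVC against baseline, whatever the cause. This is the rule that 2.1 and 10.3.1 already give. In 10.3.1, make the CLAD-attributed version the second sensitivity analysis, in place of the one that counts all falls above 20% at 12 weeks.

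Keep the CLAD-attributed term for clinical management only, under a distinct name so that it cannot be read as the complement of responder. Leave its wording on cause and the rules on rescue and withdrawal unchanged.

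The cost is wording in the protocol and the analysis plan, settled before the endpoint is analysed by arm. The downside is small: some reversible non-CLAD falls will count as non-response, in both arms.
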